5.3. Changes from the SAP Version 2.0 (17 November 2017) to Version 3.0

Changes from SAP Version 2.0 (17 November 2017) include:

- **Section 1.1:** The purpose of this document was updated for an updated report on the clinical efficacy and safety of tagraxofusp, emphasizing both the Stage 4 results that were not previously reported and the overall conclusions from the duration of the trial. Details are included in [Section 3.13.3](#) and [3.13.4](#).
- **Section 1.2:** Details on stages previous to Stage 4 were removed. Additional information on responses to be used in efficacy analyses were detailed in [Section 1.2.5.1](#).
- **Section 2.1:** The Per-Protocol Population was removed. Sensitivity analyses were also removed.
- **Section 3.5:** Methods of pooling data were updated to emphasize Stage 4, including a pooling of Stages 3 and 4 (a permutation test described in [Section 4.3.1](#), [4.3.2](#), and [4.3.3](#)).
- **Section 3.8:** The efficacy endpoints were updated to emphasize stage 4 results and overall conclusions.
- **Section 3.9:** Subgroup analyses for efficacy among subjects that bridged to SCT and Not Bridged to SCT, as well as by baseline disease site, were added.
- **Section 4.4.2.1:** Analyses of CLS based on FDA algorithm were added.

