12.1 General Considerations

Study STML-401-0114 contains patients with both AML and first-line and R/R BPDCN. The current development strategy for SL-401 is to first pursue marketing authorization for an indication in first-line BPDCN patients, with potential additional indications in R/R BPDCN and/or AML, depending on the study results. Therefore, this statistical analysis section will focus primarily on the first-line BPDCN indication, with generally similar analytical approaches to be taken with the other potential indications upon achievement of sufficient data.

Analyses will be performed on all patients who received any quantity of SL-401 (i.e., all treated patients). The baseline value for a given variable is defined as the last measurement for the variable prior to the first infusion of SL-401. Study Day 1 for each individual patient is defined as the date the patient receives their first infusion of SL-401.

Unless otherwise stated, all analyses will be performed using SAS Version 9 and all hypothesis tests will be conducted at a two-sided significance level of 0.05 or at a one-sided significance level of 0.025. P-values will be presented with 3 decimals and p-values that are less than 0.001 will be presented as <0.001. Selected data summaries will be presented by disease (BPDCN and AML), with the primary data presentations provided for data from patients with BPDCN. For data from BPDCN patients, further categories for summarization will consist of line of therapy (first-line, R/R, and total) and dose (12 µg/kg/day and all doses). Efficacy endpoints will be summarized separately for Stage 3 patients, with an additional summary for all first-line and R/R BPDCN patients across all study stages. Stage 4 will be analyzed separately.

Continuous (non-survival related) data will be summarized using descriptive statistics: number of observations (n), mean, standard deviation (SD), median, minimum, and maximum. Time to event data will be summarized using frequency and percentage of events and censored observations. Kaplan-Meier analysis will be performed to estimate the 25th percentile, median, and 75th percentile for time to events with corresponding two-sided 95% confidence intervals.

Unless otherwise stated, confidence intervals, when presented, will be constructed at the 2-sided 95% level. For binomial variables, 95% confidence intervals will be constructed using the Clopper Exact method instead of normal approximation.

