12.2 Populations for Analysis

Safety analysis will be performed on the population of patients who have received any amount of study treatment. The primary population for the analysis of efficacy will be the modified intent-to-treat (mITT) population, consisting of those patients who are eligible based on screening criteria, and have received at least one dose of study drug. For BPDCN patients an additional criterion for mITT patients will be a confirmed diagnosis based on central pathology review. BPDCN patients in the mITT population will be said to be evaluable. Additional efficacy analyses will be performed on a per-protocol (PP) population, consisting of those patients who are in the mITT population, are compliant with all major aspects of the protocol, and have received a minimum of 2 cycles of study treatment.

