2. PATIENT POPULATION

2.1. Population Definitions

The following patient populations will be evaluated and used for presentation and analysis of the data:

- Modified Intent-to-Treat (mITT) Population: All patients who are eligible based on the screening criteria and who received at least 1 dose of tagraxofusp. For BPDCN patients to be eligible for mITT they must also have diagnosis of disease based on central pathology review to be “Confirmed” or “Inconclusive: Likely BPDCN”. Patients who meet the criteria for mITT will be considered “evaluable.” Patients will be grouped according to the planned dose level at time of enrollment.
- Immunogenicity Population: All patients enrolled in the study who received at least 1 dose of tagraxofusp and had sufficient samples to permit immunogenicity analysis.
- Safety Population: All patients enrolled in the study who received at least 1 dose of tagraxofusp. Patients will be grouped according to the actual dose level received.

The mITT population is the primary population for the analysis of efficacy parameters. The Immunogenicity population will be used for summary of immunogenicity results. Supportive subgroup efficacy analyses will be performed in the mITT population, as described in [Section 3.9](#). When the subgroup is defined by immunogenicity parameters, the population will be mITT patients with sufficient samples collected to permit the respective analysis. The Safety population is the primary population for the analysis of safety.

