3. GENERAL STATISTICAL METHODS

3.1. Sample Size Justification

The sample size was originally planned to be approximately 40-50 patients with BPDCN, including approximately 40 previously untreated patients planned to be treated with the tagraxofusp dose as determined in the completed Stage 1 of this study (12 µg/kg/day). In addition, up to approximately 36 patients with R/R AML were planned to be enrolled in Stage 2 of the study. These sample sizes were not based on a formal statistical approach but were considered reasonable to accomplish study objectives for these phases of the trial.

In Stage 3, a sufficient number of patients were enrolled to ensure 10 evaluable patients would be included, with evaluable patients in the mITT population, defined as patients with a diagnosis

of BPDCN, as confirmed via central pathology review, and who received at least 1 dose of tagraxofusp. [REDACTED]

[REDACTED] The primary efficacy analysis for Stage 3 compared the lower bound of a 2-sided 95% Clopper Exact confidence interval (CI) on the observed CR rate to a clinically meaningless value of 10%. Assuming a CR rate of at least 60%, a minimal sample size of 10 first-line BPDCN patients provided at least 90% power for the primary efficacy assessment. Due to the criteria for evaluability in the BPDCN mITT population requiring central pathology review, 13 first-line BPDCN patients were enrolled in Stage 3 between October 26, 2016 and March 17, 2017. Statistical significance was determined when the lower bound of this CI fell above the rate of 10%.

After completion of enrollment of patients with first-line BPDCN in Stage 3, 39 first-line BPDCN patients were enrolled in Stage 4 (37 treated with study drug and 2 screen failures) and 5 R/R BPDCN enrolled in this study after 29 August, 2016 were enrolled in Stage 4.

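### SAP version 3.0 specifies CR and ORR on the mITT population only; a supportive all-treated estimate is needed to show whether the rates depend on the exclusions

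*SAP*

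**What the plan says.** **SAP.** Section 2.1 states: "The mITT population is the primary population for the analysis of efficacy parameters." The definition begins "All patients who are eligible based on the screening criteria and who received at least 1 dose of tagraxofusp" and, for BPDCN, adds a central pathology result that is either confirmed or inconclusive but likely. Table 3-1 lists the planned efficacy analyses for first-line and R/R BPDCN at 12 µg/kg/day. Its population row reads mITT throughout. Section 5.3 lists, among the changes from version 2.0, the deletion of the per-protocol population, and continues: "Sensitivity analyses were also removed." It does not say what those sensitivity analyses were.

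**Protocol.** Section 12.2 states: "The primary population for the analysis of efficacy will be the modified intent-to-treat (mITT) population." It then adds a second efficacy set: "Additional efficacy analyses will be performed on a per-protocol (PP) population." Section 12.1 carries a general convention: "Analyses will be performed on all patients who received any quantity of SL-401 (i.e., all treated patients"). Section 12.3 says that all first-line BPDCN patients enrolled in the Stage 3 window belong to the Stage 3 analysis, and gives avoidance of selection bias as the reason. Section 8.3 has site pathology make or confirm the diagnosis at screening, with material going to the central pathologist after enrolment.

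**Numbers.** SAP 3.1 reports that "13 first-line BPDCN patients were enrolled in Stage 3 between October 26, 2016 and March 17, 2017" and links this to the central-review requirement, the aim being at least 10 evaluable patients. It also reports 37 first-line patients treated in Stage 4. Neither document gives an mITT count or a CR count.

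**The concern.** mITT starts from patients who have had at least one dose. Anyone removed by the eligibility or pathology condition is therefore a treated patient leaving the denominator. The trial is open-label and single-arm, and the investigator assesses response. No deadline is stated for the pathology decision relative to dosing or response, and no masking of the central pathologist to outcome is described. The rule itself also varies: protocol 12.2 asks for a confirmed diagnosis, the SAP also accepts likely cases, and the protocol synopsis omits the eligibility condition that 12.2 includes.

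None of this shows bias. It does mean that the denominator rests on judgements that could be made late, and the usual check is the same rate on all treated patients. With the per-protocol and sensitivity analyses gone, the SAP plans no CR or ORR rate on a second denominator. The Stage 3 versus Stage 4 comparison, meant to support similarity of the two formulations, also rests on CR, and Table 3-1 places that pool on mITT.

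**Working it through.** **Step 1. Reproduce the plan's own figure.** Inputs from SAP 3.1 and protocol 12.6.2: n = 10, benchmark 10%, assumed CR rate 60%, success if the lower limit of the two-sided 95% Clopper-Pearson interval exceeds 10%. The lower limit for r responders of n is the 2.5% quantile of Beta(r, n − r + 1).

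- 3/10 has lower limit 6.7% and fails; 4/10 has 12.2% and passes. The rule is at least 4 of 10.
- Type I error: P(X ≥ 4 | n = 10, p = 0.10) = 0.0128.
- Power: P(X ≥ 4 | n = 10, p = 0.60) = 0.945, which agrees with the stated figure of at least 90%.

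No stated figure is wrong.

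**Step 2. Effect on the Stage 3 estimate.** Assumptions, because the counts are not given: all 13 enrolled patients were treated, and 10 were evaluable. Write x for CRs among the evaluable patients and j (0 to 3) for CRs among the excluded. The mITT rate is x/10 and the all-treated rate is (x + j)/13.

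| mITT | All treated, j = 0 | All treated, j = 3 |
|---|---|---|
| 6/10 = 60.0% (26.2–87.8) | 6/13 = 46.2% (19.2–74.9) | 9/13 = 69.2% (38.6–90.9) |
| 7/10 = 70.0% (34.8–93.3) | 7/13 = 53.8% (25.1–80.8) | 10/13 = 76.9% (46.2–95.0) |

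For 7/10 the shift lies between 53.8 − 70.0 = −16.2 and 76.9 − 70.0 = +6.9 percentage points. The direction is not known. With 11 or 12 evaluable the range is narrower, and with 13 it is zero.

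**Step 3. Effect on the Stage 3 test.** On 13 patients, 4/13 has lower limit 9.1% and fails; 5/13 has 13.9% and passes. Comparing both denominators for 10 to 12 evaluable patients, the result can differ only here:

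| mITT result | All-treated result that differs |
|---|---|
| 4/10 passes (12.2%) | 4/13 fails, if no excluded patient responded |
| 4/11 passes (10.9%) | 4/13 fails, if no excluded patient responded |
| 4/12 fails (9.9%) | 5/13 passes, if the one excluded patient responded |
| 3/10 fails (6.7%) | 5/13 or 6/13 passes, if 2 or 3 responded |
| 3/11 fails (6.0%) | 5/13 passes, if both responded |
| 2/10 fails (2.5%) | 5/13 passes, if all 3 responded |

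A pass turns into a failure only with exactly 4 CRs among 10 or 11 evaluable patients. At the design rate of 60%, exactly 4 of 10 has probability C(10,4) × 0.6⁴ × 0.4⁶ = 0.111. With 5 or more CRs among evaluable patients, both denominators pass.

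**Step 4. Stage 4 first-line.** Input: 37 treated (SAP 3.1). Assumptions: 0 to 5 excluded, and a CR rate of about 60% among the evaluable. With 5 excluded, 19/32 = 59.4% on mITT becomes 19/37 = 51.4% if none of the five responded, or (19 + 5)/37 = 64.9% if all did. With none excluded, both rates are 22/37 = 59.5%.

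**The case against.** The strongest reply is that the SAP follows the protocol. Section 12.2 is the specific rule: mITT is primary for efficacy, and per-protocol is the only additional efficacy set it names. The sentence in 12.1 is a general convention that mentions neither CR nor ORR. A reader might infer that version 3.0 deleted an all-treated CR rate that the protocol required. The documents do not support that: SAP version 2.0 is not available, the removed sensitivity analyses are not described, and no protocol section names an all-treated CR analysis. The deletion that can be traced to the protocol is the per-protocol analysis.

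A reader might also infer that patients were removed after their response was known. That too goes beyond the text. Eligibility rests on screening criteria, central review concerns the baseline diagnosis and is not done by the investigator who rates response, and the stated timing is only after enrolment.

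Further, SAP 4.1 tabulates the numbers treated and in each population, and SAP 4.3 keeps by-patient efficacy listings, so the rate could probably be rebuilt by hand. An exploratory rate including CRi and optional IRC-based analyses also remain.

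These replies stand against any charge of a protocol breach. They do not supply the missing estimate. Primary does not mean sole, and 12.2 itself planned a second efficacy set that is now gone. The CRi and IRC analyses change the endpoint or the assessor and are not specified on an all-treated denominator. Protocol 12.3 still promises inclusion of all enrolled first-line patients, which fits poorly with an mITT-only plan.

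**Conclusion.** The point holds as a gap in supportive analysis, together with an inconsistency among protocol 12.1, 12.2 and 12.3. It is not a departure from a required analysis. The SAP plans CR and ORR on mITT alone, and the exclusions that define mITT may be decided after treatment.

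Under the assumption of 13 treated and 10 evaluable, the illustrative Stage 3 rate of 70.0% could lie anywhere from 53.8% to 76.9% on all treated patients. For Stage 4, under the stated assumptions, the all-treated range is 51.4% to 64.9%. These are ranges built on assumed counts, not estimates of bias. If nobody was excluded, the difference is zero.

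A reader might take this to cast doubt on the pivotal test. It does not. SAP 3.13.3 places that analysis after the 25 September 2017 cutoff, before version 3.0, and the result would depend on the denominator only with 4 or fewer CRs among evaluable patients. The point matters mainly for the updated Stage 4 and pooled report that this SAP governs. The change should be made, and it leaves the primary analysis as it is.

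**What to change.** 1. Keep mITT as the primary efficacy population.
2. In Table 3-1 and SAP 4.3.1, add supportive CR (CR + CRc) and ORR with exact 95% intervals for all treated BPDCN patients whose planned dose was 12 µg/kg/day, by line of therapy, for Stage 3 (first-line only), Stage 4 and the pooled columns. Treated patients without central acceptance stay in the denominator. Use the planned-dose grouping of mITT: the Safety population groups by actual dose, and using it unchanged would mix regrouping by dose with the effect of the exclusions.
3. List each treated patient excluded from mITT with the reason, the date of the pathology or eligibility decision, and best response.
4. Reconcile protocol 12.1 and 12.3 with 12.2, so that it is clear which analyses use all treated patients.

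The cost is a few table rows and one listing, mostly from data already collected. The sponsor also accepts a supportive figure that may be less favourable than the mITT rate.

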7. STUDY FLOW CHARTS

The following Study Flow Charts are from Protocol Amendment 8 and Amendment 9.

Table 7-1: Study Events Schedule for Cycle 1 (Study Day -14 to Study Day 21): Stage 1 (All Pts) & Stage 2 (AML Pts: Arm A)

Tests and Observations	Study Day -14 to -4	Cycle 1					
		Study Day -1 to 0	Study Days 1-5 (Up to Study Day 10 if Infusion(s) Held) tagraxofusp Treatment		Study Day 8±3 ^(q) and 15±3	Study Day 21±7	Study Day 28±7, Then Every 7±3 Days
	Screening	Pre-treatment	Pre-Infusion	Infusion		End of Cycle	Delayed End of Cycle for Toxicity Resolution Only if Required
Informed consent form	X						
Inclusion/exclusion criteria	X						
Medical history including prior therapy, concomitant medications	X						
Concomitant Medications		X			X	X	X
ECOG performance status	X					X	X
Physical examination	X	X			X	X	
Pregnancy test ^(a)	X						
Vital signs and weight ^(b)	X	X	X	X	X	X	X
12-lead ECG ^(c)	X	X	X	X (Infusions 1, 5)		X	X
ECHO or MUGA scan ^(d)	X						
Hematology ^(e)	X	X	X		X	X	X
Serum electrolytes ^(f)	X	X	X		X	X	X
Serum albumin ^(g)	X	X	X		X	X	X
Serum chemistry ^(h)	X	X	X		X	X	X
Coagulation parameters: PT/INR, aPTT	X		X		X	X	X
Urinalysis ⁽ⁱ⁾	X		X (Infusion 1)		X	X	X
Tumor response assessment: Bone marrow aspiration ± biopsy ^(j)	X					X	

Tumor response assessment: CT scan(k)	X						
Tumor response assessment: Skin, including biopsies and/or photographs(l)	X					X	
Tumor response assessment: Peripheral blood						X	
Translational assessment: Peripheral blood (m)			X (Infusions 1, 5)		X	X	
Administration of premeds (n)			X				
Tagraxofusp administration(o)				X			
Tests and Observations		Cycle 1					
		Study Day -14 to -4	Study Day -1 to 0	Study Days 1-5 (Up to Study Day 10 if Infusion(s) Held) tagraxofusp Treatment		Study Day 21±7	Study Day 28±7, Then Every 7±3 Days
	Screening	Pre-treatment	Pre-Infusion	Infusion		Study Day 8±3^(q) and 15±3	Delayed End of Cycle for Toxicity Resolution Only if Required
Pharmacokinetic sampling ^(p)			X (Infusions 1, 5)	X (Infusions 1, 5)			
Immunogenicity sampling ^(q)			X (Infusion 1)		X (Day 15)	X	
AE and SAE monitoring			X	X	X	X	X

- (a) Urine or serum pregnancy test must be performed within 1 week prior to treatment in women of childbearing potential.
- (b) Vital signs should be performed after patient is sitting for 3-5 minutes. If during dosing period, vital signs should be taken immediately prior to infusion, immediately after completion of infusion, and 30, 60, and 240 minutes post-infusion.
- (c) All patients will have a 12-lead Electrocardiogram (ECG) performed at the screening visit and pre-treatment visit, as well as Day 21 (and Day 28 only if delayed end of cycle) of each cycle. During the days when patients are undergoing PK sampling (Cycle 1, infusions 1 and 5; Cycle 3, infusions 1 and 5), an ECG will be performed at 3 distinct time points (triplicates) within 5 minutes prior to each PK sample collection pre-infusion and at 30 and 60 minutes post-infusion (see (p) and Table 10 in the protocol).
- (d) Multigated Acquisition Scan (MUGA) or 2-D ECHO to quantify left ventricular ejection fraction (LVEF). Must be completed within 28 days prior to start of first cycle of study treatment.
- (e) To be collected prior to tagraxofusp infusion if during dosing period. Hematology includes White blood cell (WBC) count, differential white cell count, red blood cell count, hematocrit, hemoglobin and platelet count.
- (f) To be collected prior to tagraxofusp infusion if during dosing period. Electrolytes include sodium, potassium, bicarbonate, chloride, blood urea nitrogen (BUN), and creatinine.

- (g) To be collected prior to tagraxofusp infusion if during dosing period. Serum albumin may be a component of the chemistry panel (h). See protocol for administration of albumin if serum albumin decreases to <3.0 mg/dL during treatment days or in the immediate post-treatment period.
- (h) To be collected prior to tagraxofusp infusion if during dosing period. Serum electrolytes and chemistry: Sodium, potassium, bicarbonate, chloride, BUN, creatinine, glucose, alanine aminotransferase (ALT), albumin, alkaline phosphatase (ALP), aspartate aminotransferase (AST), bilirubin (total, direct, and indirect), calcium, creatine phosphokinase (CPK), magnesium, lactate dehydrogenase (LDH), phosphate, total protein, uric acid
- (i) To be collected prior to tagraxofusp infusion if during dosing period. Urinalysis includes appearance, color, pH, specific gravity, ketones, leukocytes, protein, glucose, bilirubin, urobilinogen, and occult blood.
- (j) Morphology and differential WBC/blast count on aspirate. Baseline must be performed within 14 days prior to the first administration of tagraxofusp. Subsequent bone marrow aspirates (\pm biopsy) will be performed 21 (\pm 7) days after the start of Cycles 1 and 2, and at the Investigator's discretion thereafter until there is evidence of relapsed or progressive disease. If the Cycle 1 (Day 21 [\pm 7]) bone marrow aspirate (\pm biopsy) is empty, hypocellular, or inadequate, a bone marrow examination should be repeated within 7 (\pm 7) days to document response. During Stage 2, AML patients (and BPDCN patients with evidence of bone marrow involvement prior to study treatment) will also have bone marrow evaluations following Cycles 4 and 6, and at the Investigator's discretion prior to end of treatment and thereafter. Any additional bone marrow aspirate (\pm biopsy) remaining after the sample is aliquoted for tumor assessment will be collected for translational/correlative assessment. In general, the bone marrow aspirate will be prioritized for tumor assessment over translational/correlative assessment. However, submission of bone marrow aspirate material for translational/correlative assessment (5 mL, larger when feasible) is required both for a pre-treatment (baseline) specimen, and at the end of Cycle 1. If CD123 flow cytometry or IHC stain was performed on the bone marrow aspirations (\pm biopsy), the results should be recorded in the eCRF.
- (k) BPDCN patients only. Baseline must be performed within 14 days prior to the first administration of tagraxofusp. Subsequent CT scans will be performed 21 (\pm 3) days after the start of Cycle 2 and 4 and 21 (\pm 7) days after the start of every 4th cycle thereafter until there is evidence of relapsed or progressive disease. Baseline CT scans should be full-body, whereas follow-up scans should document response of index lesions.
- (l) BPDCN patients only, with biopsies and/or photographs as indicated, for patients with skin involvement. Baseline must be performed within 14 days prior to the first administration of tagraxofusp. Subsequent skin assessments will be performed 21 (\pm 3) days after the start of Cycles 1 and 2 and 21 (\pm 7) days after the start of every 2nd cycle thereafter (Cycles 4, 6, etc.) until there is evidence of relapsed or progressive disease.
- (m) Cycle 1 and 3, and at end of treatment, Translational Assessment should be collected at Infusion 1 (Day 1), Infusion 5 (Day 5, 6, 7; if Infusion 5 does not occur by Day 8, please obtain this specimen on Day 8) and days 15, 21 (\pm 3 days, but must occur prior to start of subsequent treatment cycle). (n) Refer to protocol Section 7.5.3.1 – Premedication
- (o) Following treatment with premedication, tagraxofusp will be administered as a 15-minute infusion for the first 5 consecutive days of a 21-day cycle. Individual tagraxofusp infusions may be delayed to allow for toxicity resolution, all infusions should be completed within 10 days and fewer than 5 infusions are permitted in settings of incipient CLS or hepatotoxicity. Patients must be monitored for 4 hours post infusion.
- (p) Plasma samples (6 mL each) will be collected immediately prior to the start of the infusion of tagraxofusp, immediately after end of infusion (time recorded), then 15, 30, 45, 60, 90, 120, 180, and 240 minutes after completion of the infusion during infusions 1 (ie, Study Day 1) and 5 (ie, Study Day 5) (see (c) and Table 10 in the protocol).
- (q) Blood samples (10 mL) will be collected for the detection of tagraxofusp reactive antibodies according on Day 1 (pre-infusion), Day 15, and Day 21 (if patient is to receive Cycle 2, can be Day 1, pre-infusion for Cycle 2). If infusions are held, please collect a sample within 3 \pm 3 days after the last tagraxofusp infusion(s) of the cycle.

Table 7-2: Study Events Schedule for Cycles 2-6 and Subsequent Cycles: Stage 1 (All Pts) & Stage 2 (AML Pts: Arm A)

Tests and Observations	Cycle 2+					Safety: Through 30 Days After Last Infusion	Survival: Every 90 Days After Last Infusion
	Days 1-5 (Up to Day 10 if Infusion(s) Held) Tagraxofusp Treatment		Day 8±3 ^(q) and 15±3	Day 21±3	Day 28±3, Then Every 7±3 days		
	Pre-Infusion	Infusion		End of Cycle	Delayed End of Cycle for Toxicity Resolution Only if Required		
Medical history including prior therapy, concomitant medications							
Concomitant Medications			X	X	X		
ECOG performance status				X	X	X	
Physical examination			X	X		X	
Vital signs and weight ^(a)	X	X	X	X	X	X	
12-lead ECG ^(b)	X	X (Cycle 3, Infusions 1, 5)		X	X		
Hematology ^(c)	X		X	X	X		
Serum electrolytes ^(d)	X		X	X	X		
Serum albumin ^(e)	X		X	X	X		
Serum chemistry ^(f)	X		X	X	X		
Coagulation parameters: PT/INR, aPTT	X		X	X	X		
Urinalysis ^(g)	X (Infusion 1)		X	X	X		
Tumor response assessment: Bone marrow aspiration ± biopsy ^(h)				X ^(h)			
Tumor response assessment: CT scan ⁽ⁱ⁾				X			
Tumor response assessment: skin, including biopsies and/or photographs ^(j)				X			

Tumor response assessment: peripheral blood				X (k)				
Translational assessment: Peripheral blood (l)	X (Infusions 1,5)		X	X		X		
Administration of premeds (m)	X							
Tagraxofusp administration(n)		X						
Pharmacokinetic sampling ^(o)	X (Cycle 3, Infusions 1, 5)	X (Cycle 3, Infusions 1, 5)						
Immunogenicity sampling ^(p)	X (Infusion 1)			X				
Tests and Observations	Cycle 2+					End of Treatment	Safety: Through 30 Days After Last Infusion	Survival: Every 90 Days After Last Infusion
	Days 1-5 (Up to Day 10 if Infusion(s) Held) Tagraxofusp Treatment		Day 8±3^(q) and 15±3	Day 21±3	Day 28±3, Then Every 7±3 days			
	Pre- Infusion	Infusion		End of Cycle	Delayed End of Cycle for Toxicity Resolution Only if Required			
AE and SAE monitoring	X	X	X	X	X		X	
Long-term follow-up(q)							X	X

- (a) Vital signs should be performed after patient is sitting for 3-5 minutes. If during dosing period, vital signs should be taken immediately prior to infusion, immediately after completion of infusion, and 30, 60, and 240 minutes post-infusion.
- (b) All patients will have a 12-lead ECG performed at the screening visit and pre-treatment visit, as well as Day 21 (and Day 28 only if delayed end of cycle) of each cycle. During the days when patients are undergoing PK sampling (Cycle 1, infusions 1 and 5; Cycle 3, infusions 1 and 5), an ECG will be performed at 3 distinct time points (triplicates) within 5 minutes prior to each PK sample collection pre-infusion and at 30 and 60 minutes post-infusion (see footnote (n) and Table 10 in the protocol).
- (c) To be collected prior to tagraxofusp infusion if during dosing period. Hematology includes WBC count, differential white cell count, red blood cell count, hematocrit, hemoglobin and platelet count.
- (d) To be collected prior to tagraxofusp infusion if during dosing period. Electrolytes include sodium, potassium, bicarbonate, chloride, BUN, and creatinine.
- (e) To be collected prior to tagraxofusp infusion if during dosing period. Serum albumin may be a component of the chemistry panel (f). See protocol for administration of albumin if serum albumin decreases to <3.0 mg/dL during treatment days or in the immediate post-treatment period.
- (f) To be collected prior to tagraxofusp infusion if during dosing period. Serum electrolytes and chemistry: Sodium, potassium, bicarbonate, chloride, BUN, creatinine, glucose, ALT, ALP, AST, bilirubin (total, direct, and indirect), calcium, CPK, magnesium, LDH, phosphate, total protein, uric acid
- (g) To be collected prior to tagraxofusp infusion if during dosing period. Urinalysis includes appearance, color, pH, specific gravity, ketones, leukocytes, protein, glucose, bilirubin, urobilinogen, and occult blood.
- (h) Morphology and differential WBC/blast count on aspirate. Bone marrow aspirates (± biopsy) will be performed 21 (±7) days after the start of Cycle 2, and, in Stage 1, at the Investigator's discretion prior to end of treatment and thereafter until there is evidence of relapsed or progressive disease. In Stage 1, submission of aspirate (5 mL or greater) for translational/correlative assessment at timepoints subsequent to Cycle 1 is strongly encouraged, whenever feasible. During Stage 2, AML patients (and BPDCN patients with evidence of bone marrow involvement prior to study treatment) will also have bone marrow evaluations following Cycles 4 and 6 and then every 3 months from Months

6-12; every 6 months from 12 to 24 months; and every 12 months thereafter until there is evidence of relapsed or progressive disease. In Stage 2, any additional bone marrow aspirate (\pm biopsy) remaining after the sample is aliquoted for tumor assessment will be collected for translational/correlative assessment. The bone marrow aspirate will be prioritized for tumor assessment over translational/correlative assessment. If CD123 flow cytometry or IHC stain was performed on the bone marrow aspirations (\pm biopsy), the results should be recorded in the eCRF.

- (i) BPDCN patients only. Baseline must be performed within 14 days prior to the first administration of tagraxofusp. In Stage 1, subsequent CT scans will be performed 21 (\pm 7) days after the start of Cycle 2 and 4 and 21 (\pm 7) days after the start of every 4th cycle thereafter until there is evidence of relapsed or progressive disease. Baseline CT scans should be full-body, whereas follow-up scans should document response of index lesions.
- (j) BPDCN patients only, with biopsies and/or photographs as indicated, for patients with skin involvement. Baseline must be performed within 14 days prior to the first administration of tagraxofusp. Subsequent skin assessments will be performed 21 (\pm 7) days after the start of Cycles 1 and 2 and 21 (\pm 7) days after the start of every 2nd cycle thereafter (Cycles 4, 6, etc.) until evidence of relapsed or progressive disease. Quantification of disease burden via the mSWAT is required at the time of each skin assessment.
- (k) Patients with evidence of peripheral blasts at baseline will have peripheral blood samples collected 21 (\pm 7) days after the start of Cycles 1 and 2 and 21 (\pm 7) days after the start of every 2nd cycle thereafter (Cycles 4, 6, etc.) until there is evidence of relapsed or progressive disease.
- (l) Cycle 1 and 3, and at end of treatment, Translational Assessment should be collected at Infusion 1 (Day 1) and Infusion 5 (Day 5, 6, 7; if Infusion 5 does not occur by Day 8, please obtain this specimen on Day 8) and Days 15, 21 (\pm 3 days, but must occur prior to start of subsequent treatment cycle). (m) Refer to protocol Section 7.5.3.1 – Premedication
- (n) Following treatment with premedication, tagraxofusp will be administered as a 15-minute infusion for the first 5 consecutive days of a 21-day cycle. Individual tagraxofusp infusions may be delayed to allow for toxicity resolution; all infusions should be completed within 10 days and fewer than 5 infusions are permitted in settings of incipient CLS or hepatotoxicity. Patients must be monitored for 4 hours post infusion.
- (o) Plasma samples (6 mL each) will be collected immediately prior to the start of the infusion of tagraxofusp, immediately after end of infusion (time recorded), then 15, 30, 45, 60, 90, 120, 180, and 240 minutes after the start of the infusion during infusions 1 (ie, Day 1) and 5 (ie, Day 5) of Cycle 3 (see footnote (b) and Table 10 in the protocol).
- (p) Blood samples (10 mL) will be collected for the detection of tagraxofusp reactive antibodies according on Day 1 (pre-infusion), Day 15, and Day 21 (if patient is to receive additional cycles, can be Day 1, pre-infusion for next cycle). If infusions are held, please collect a sample within 3 \pm 3 days the last tagraxofusp infusion(s) of the cycle.
- (q) After the follow-up visit, patients will then be followed every 90 days for survival status. The survival follow-up may be by telephone contact. If the patient is in CR/PR at the time of discontinuation, disease assessments should continue to be performed as described in protocol Section 8.11 on an every 6-week basis (\pm 1 week) through 6 months post-C1D1 and then on an every 90-day basis or until, in the judgment of the Investigator, there is evidence of relapsed or progressive disease.

Table 7-3: Study Events Schedule for Cycles 1 & 2 (Study Day -14 to Study Day 21): BPDCN (Arm B) Patients in Stage 2

Tests and Observations	Study Day -14 to -4	Cycles 1 & 2					
		Study Day -1 to 0	Cycle Days 1-5 (Up to Study Day 10 if Infusion(s) Held) Tagraxofusp Treatment		Study Day 8±3 ^(q) and 15±3	Cycle Day 21±7	Cycle Day 28±7, Then Every 7±3 Days
		Screening	Pre- treatment	Pre-Infusion		End of Cycle	Delayed End of Cycle for Toxicity Resolution Only if Required
Informed consent form	X						
Inclusion/exclusion criteria	X						
Medical history including prior therapy, concomitant medications	X						
Concomitant Medications		X			X	X	X
ECOG performance status	X					X	X
Physical examination	X	X			X	X	
Pregnancy test ^(a)	X						
Vital signs and weight ^(b)	X	X	X	X	X	X	X
12-lead ECG ^(c)	X	X	X	X (Infusions 1, 5)		X	X
ECHO or MUGA scan ^(d)	X						
Hematology ^(e)	X	X	X		X	X	X
Serum electrolytes ^(f)	X	X	X		X	X	X
Serum albumin ^(g)	X	X	X		X	X	X
Serum chemistry ^(h)	X	X	X		X	X	X
Coagulation parameters: PT/INR, aPTT	X		X		X	X	X
Urinalysis ⁽ⁱ⁾	X		X (Infusion 1)		X	X	X
Tumor response assessment: Bone marrow aspiration ± biopsy ^(j)	X					X	
Tumor response assessment: CT scan ^(k)	X					X (Cycle 2) (k)	

Tumor response assessment: Skin, including biopsies and/or photographs ^(l)	X					X	
Tumor response assessment: Peripheral blood						X	
Translational assessment: Peripheral blood (m)							
Administration of premeds (n)			X				
Tagraxofusp administration ^(o)				X			
Pharmacokinetic sampling ^(p)			X (Infusions 1, 5)	X (Infusions 1, 5)			
Tests and Observations		Cycles 1 & 2					
		Study Day -14 to -4	Study Day -1 to 0	Cycle Days 1-5 (Up to Study Day 10 if Infusion(s) Held) Tagraxofusp Treatment	Study Day 8±3 ^(q) and 15±3	Cycle Day 21±7	Cycle Day 28±7, Then Every 7±3 Days
	Screening	Pre-treatment	Pre-Infusion	Infusion		End of Cycle	Delayed End of Cycle for Toxicity Resolution Only if Required
Immunogenicity sampling ^(q)			X (Infusion 1)		X (C1D15 only)	X	
Vision Assessment	X						
AE and SAE monitoring			X	X	X	X	X

- (a) Urine or serum pregnancy test must be performed within 1 week prior to treatment in women of childbearing potential.
- (b) Vital signs should be performed after patient is sitting for 3-5 minutes. If during dosing period, vital signs should be taken immediately prior to infusion, immediately after completion of infusion, and 30, 60, and 240 minutes post-infusion.
- (c) All patients will have a 12-lead ECG performed at the screening visit and pre-treatment visit, as well as Day 21 (and Day 28 only if delayed end of cycle) of each cycle. During the days when patients are undergoing PK sampling (Cycle 1, infusions 1 and 5; Cycle 3, infusions 1 and 5), an ECG will be performed at 3 distinct time points (triplicates) within 5 minutes prior to each PK sample collection pre-infusion and at 30 and 60 minutes post-infusion (see (p) and Table 10 in the protocol).
- (d) MUGA or 2-D ECHO to quantify LVEF. Must be completed within 28 days prior to start of first cycle of study treatment.
- (e) To be collected prior to tagraxofusp infusion if during dosing period. Hematology includes WBC count, differential white cell count, red blood cell count, hematocrit, hemoglobin and platelet count.
- (f) To be collected prior to tagraxofusp infusion if during dosing period. Electrolytes include sodium, potassium, bicarbonate, chloride, BUN, and creatinine.
- (g) To be collected prior to tagraxofusp infusion if during dosing period. Serum albumin may be a component of the chemistry panel (h). See protocol for administration of albumin if serum albumin decreases to <3.0 mg/dL during treatment days or in the immediate post-treatment period.
- (h) To be collected prior to tagraxofusp infusion if during dosing period. Serum electrolytes and chemistry: Sodium, potassium, bicarbonate, chloride, BUN, creatinine, glucose, ALT, albumin, ALP, AST, bilirubin (total, direct, and indirect), calcium, CPK, magnesium, LDH, phosphate, total protein, uric acid

- (i) To be collected prior to initial tagraxofusp infusion of the cycle. Urinalysis includes appearance, color, pH, specific gravity, ketones, leukocytes, protein, glucose, bilirubin, urobilinogen, and occult blood.
